### 10.3 Unanticipated Problems

Any unexpected, serious adverse effect on health or safety of participants having implications for the conduct of the study (e.g., requiring a significant and usually safety-related, change in the protocol such as revising inclusion/exclusion criteria or including a new monitoring requirement, informed consent, or investigator's brochure) not previously identified in nature, severity, or degree of incidence in the study protocol, informed consent or investigator's brochure.

### 10.4 Adverse Event Relatedness

The clinician's assessment of an AE's relationship to the study CTM is part of the documentation process, though does not determine whether it is reported. Clinical observations suspected to be an AE must be reported. For all collected AEs, the clinician who examines and evaluates the participant will determine the AE's causality based on temporal relationship and clinical judgment. The degree of certainty of causality will be graded as:

- **Definitely Related:** There is unequivocal evidence of a causal relationship, and other possible contributing factors can be ruled out. The timing of a clinical event, including an abnormal laboratory test result, is related to the delivery of the study CTM and is not explained by a concurrent disease or other pharmaceuticals or chemicals. The response to withdrawal of the study CTM (de-challenge) should be clinically plausible. The event must be pharmacologically or phenomenologically definitive. The AE is expected to be reproduced by an appropriate re-challenge procedure.

	PILL SWALLOW STUDY PROTOCOL	Doc No.:	CP-0003
		Revision:	C
		Page:	Page 23 of 24

- **Probably Related:** There is evidence of a causal relationship, and the influence of other factors is unlikely. The clinical event, including an abnormal laboratory test result, occurs within a reasonable time after the administration of the study CTM, is unlikely to be due to a concurrent disease or other pharmaceuticals or chemicals, and responds as expected to a de-challenge.
- **Possibly Related:** There is some evidence in favor of a causal relationship (e.g., the event occurred within a reasonable time after administration of the study CTM), though other factors may have contributed to the event (e.g., the participant's clinical condition, other concomitant events). Although an AE may be listed as "possibly related" soon after its identification, it may be flagged as requiring more information and later upgraded to "probably" or "definitely" related, as appropriate.
- **Probably Not Related:** A clinical event, including an abnormal laboratory test result, whose temporal relationship to the study CTM administration makes a causal relationship improbable (e.g., the event did not occur within a reasonable time after administration of the study CTM) and where other pharmaceuticals or chemicals, or an underlying disease provide a satisfactory explanation (e.g., the participant's clinical status, a concomitant treatment).
- **Unrelated:** The AE is completely independent of the administration of the study CTM, or the event is unequivocally due to another cause. There must be an alternate, definitive cause documented by the clinician.

## 10.5 Adverse Event Severity

Adverse event severity will be categorized using the following definitions:

- **Mild:** Events require minimal or no treatment and do not interfere with the participant's daily activities.
- **Moderate:** Events result in minor inconvenience or concern with the therapy. Moderate events may interfere with some functions.
- **Severe:** Events interrupt a participant's usual daily activity and may require systemic drug therapy or other treatment. Severe events may be life-threatening or incapacitating.

## 10.6 Deaths

During the study, all deaths must be reported to Rani Therapeutics within 24 hours. A copy of the participant's death records, medical records for the events that led to the participant's death, and a death certificate (if available) should be provided.

## 10.7 Anticipated Adverse Events

Known potential risks of swallowing the Mock-RP include:

- Oropharyngeal symptoms (coughing, gagging, etc.)

- Airway obstruction due to accidental aspiration
- Dysphagia
- Nausea/vomiting
- Dyspepsia

### 10.8 Adverse Event Reporting

All adverse events occurring from the start of any study specific screening procedures must be recorded in the eCRF. Adverse events identified and reported in this study will be classified in accordance with the adverse event diagnosis and reported to the IRB per local requirements.

AEs must be recorded on the eCRF and be described by (a) duration (start and resolution dates); (b) signs and symptoms; (c) final event diagnosis; (d) event severity; (e) Investigator's clinical opinion on the relationship to the study CTM; (f) action taken to resolve the event; (g) outcome of the event; and (h) whether or not such event is considered to have been serious and/or unanticipated.

Adverse events should be reported according to their underlying cause, if known. Multiple symptoms related to a single diagnosis should not be reported as separate AEs. Only concomitant AEs that are unrelated to each other (in the clinician's judgment) should be reported as separate events.

## 11 BENEFIT-RISK ANALYSIS

The use of the Mock-RP may be associated with adverse effects; however, in this pill swallow study, the overall and serious adverse effect risks are anticipated to be low and very low, respectively. Most adverse effects, if any, are likely to occur during swallowing of the Mock-RP.

### 11.1 Potential Risks

There are risks to the participant associated with study participation. Risks are associated with administration of the Mock-RP (defined in section 10.7) and participation in a clinical study. The greatest risk of participating in this clinical study is loss of confidentiality. Every attempt will be made to ensure participant confidentiality.

### 11.2 Potential Benefits

There are no anticipated benefits from participation in this study other than free medical tests. Future clinical use of the RaniPill™ Capsule is likely to improve participants' quality of life and increase their compliance with treatment by offering a needle-free alternative to repeated injections.

## 12 EARLY TERMINATION

Rani Therapeutics may terminate Investigator and/or site participation in the study for issues including but not limited to the following:

- Evidence of an Investigator's failure to maintain adequate clinical standards
- Evidence of an Investigator or staff's failure to comply with the CIP
- Inaccuracy or late submission of data forms
- Conditions of approval imposed by the reviewing IRB
- Evidence of safety concerns
- Change of staff at site that adversely impacts study conduct

Any evident pattern of non-compliance with respect to these standards will have corrective actions implemented. If corrective actions are not subsequently undertaken, the clinical site will be asked to withdraw from the study and their site may be replaced.

If Rani Therapeutics terminates or prematurely suspends the study, the investigators will be promptly informed of the rationale. In the case of study termination or suspension for reasons other than a temporary IRB approval lapse, the investigator will promptly inform the IRB. In the case of study termination, the investigator must inform the participants.

If the investigator terminates or suspends the study without the prior agreement of Rani Therapeutics, the investigator will promptly inform Rani Therapeutics and provide a detailed written explanation of the termination or suspension. The investigator will promptly inform the institution (where required per regulatory or local requirements), the IRB, and the participants.

If the IRB terminates or suspends its approval of the study, the investigator will promptly inform Rani Therapeutics and provide a detailed written explanation of the termination or suspension. Participant enrollment must stop at the site until the IRB suspension is lifted. The investigator will inform his/her institution (where required per regulatory or local requirements). The investigator will promptly inform the participants of the rationale for the study termination or suspension.

## 13 STATISTICAL METHODS

Categorical data will be summarized using frequency tables, presenting the participant counts and relative percentages. Continuous variables will be summarized by the mean, standard deviation, median, minimum and maximum. The SAS system or equivalent statistical package will be used to perform all analyses. Exact confidence intervals will be generated for estimates of proportions. Asymptotic confidence intervals will be generated for estimates of means. Except where otherwise noted, p-values of all tests will be reported without any correction for the multiplicity of tests performed.

	PILL SWALLOW STUDY PROTOCOL	Doc No.:	CP-0003
		Revision:	C
		Page:	Page 26 of 27

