#### Additional CRF Edits:

- Screening CRF: Added new exclusion criteria for allergies to mock-RaniPill components.
- Moved Pill Swallow Assessment up the form.
- Post-Swallow Questionnaire: changed VAS score from 0-10 to 0-4.
- SAE Form: added "Final Outcome" field.

Associated Files 10 Reference File(s) + 0 Implementation File(s)

Routings None specified

Approval Deadline None specified

Effectivity 2021/04/28

Expiration Date N/A (This is a permanent Change.)

Lifecycle Status... Completed

...As Of 2021/04/28 03:38:17 PM

Creator [name]

Created On 2021/04/23 06:53:40 AM

Submitter [name]

Submitted On 2021/04/23 11:30:50 AM

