## 2.3 Justification

In the previous studies, none of the participants reported any issues with swallowing the RaniPill™ Capsule. These studies were conducted in young healthy volunteers. The goal of the present study is to enroll patients of different age groups who are taking injections and will be potential candidates for the RaniPill™ Capsule when it becomes available. Understanding patient treatment preference is important in early drug development. Collecting data on patient preference of new and current therapies may help inform the benefit-risk assessment of the product (**Bouvy 2020**). The ease of swallowing oral drug therapy is a key determinant for patient acceptability. The European Medicines Agency (EMA) in 2017 released a reflection paper regarding pharmaceutical development of medicines for use in older populations and suggested swallowability and palatability are key characteristics for patient acceptability (**EMA 2017**). Ternik, et al., conducted a workshop dedicated to acceptability assessments for pediatric pharmaceutical products with similar conclusion of swallowability and palatability contributing to oral drug acceptability in pediatric patients (**Ternik 2018**). Swallowability and palatability ratings of new oral drug therapies may drive patient selection to new oral therapies vs their current injection options.

The study will test the swallowability of a pill similar in shape and size to the RaniPill™ Capsule to be referred to as Mock-RP.

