### **13.2 Sample Size Justification**

As an observational study, no hypothesis tests are planned. All data will be summarized. Nevertheless, with the sample size proposed for the study, the following levels of precision of the estimates, expressed as the width of the confidence interval, can be achieved:

1. The width of the exact 95% two-sided confidence interval for percentages will be no wider than +/- 14.5% with 50 participants contributing to the estimate of the proportion and will be no wider than +/- 8.3% with 150 participants.
2. The width of the 95% two-sided confidence interval for the mean will be equal to +/- 27.7% of the standard deviation with 50 participants contributing to the estimate of the mean and will be equal to +/- 16.0% of the standard deviation with 200 participants.

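### Section 13.2 pairs the 150-participant precision figure for a mean with 200 participants, and the normal intervals planned for means are slightly too narrow for groups of 30 to 50

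*Combined protocol and SAP*

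**What the plan says.** Section 13 (Statistical Methods) sets two general rules. For proportions: "Exact confidence intervals will be generated for estimates of proportions". For means: "Asymptotic confidence intervals will be generated for estimates of means". It adds that "Continuous variables will be summarized by the mean, standard deviation, median, minimum and maximum", and that categorical data go into frequency tables. It does not say which rule applies to the post-swallow score.

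Section 13.2 (Sample Size Justification), item 2, says the half-width for a mean will be "equal to +/- 27.7% of the standard deviation with 50 participants", and 16.0% of the SD with 200. Item 1, on percentages, uses 50 and 150 participants. The same section says that no hypothesis tests are planned.

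Sections 1.2, 5 and 7.3 allow up to 200 to be consented and up to 150 to attempt the Mock-RP, with 30 to 50 in each of three age groups. Section 4.1 also stratifies participant experience by years on injections and by injection frequency, with no minimum stratum size.

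The only description of a post-swallow score is one line in the change order's list of CRF edits: "Post-Swallow Questionnaire: changed VAS score from 0-10 to 0-4".

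**The concern.** There are two issues, one definite and one conditional.

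The definite one is that a stated precision figure does not follow from its sample size. With no hypothesis tests, the precision statements in Section 13.2 are the only quantitative support for the sample size, so they should be right.

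The conditional one is the interval method. A normal interval ignores the error in estimating the SD, so it is somewhat short in small groups. It does worse when a short bounded score piles up at one end: the interval then under-covers, may run past the end of the scale, and has zero width when all answers agree. Three of the six endpoints in Section 4.1 are participant experience by subgroup, and Section 5 intends to look at swallowing trends between subgroups. Intervals that are too short would make subgroup means look more certain, and more different, than they are.

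**Working it through.** **Inputs.** 95% two-sided level and the stated 27.7% and 16.0% (Section 13.2); asymptotic method (Section 13); 30 to 50 per age group and at most 150 swallowing (Sections 5 and 7.3); 0-4 scale (change order). The documents give no SD, expected mean or score distribution, so every score distribution below is an assumption.

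**1. The stated precision.** Half-width as a share of the SD = 1.96/√n for a normal interval, and t(0.975, n−1)/√n for a t interval.

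| n | Normal | t | Plan |
|---|---|---|---|
| 30 | 35.8% | 37.3% | not given |
| 50 | 27.7% | 28.4% | 27.7% |
| 150 | 16.0% | 16.1% | not given |
| 200 | 13.9% | 13.9% | 16.0% |

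The figure at 50 reproduces and shows that a normal, not a t, interval was used. The figure at 200 does not reproduce by either method; 16.0% is 1.96/√150. Item 1 reproduces at its own sizes: the largest exact half-widths are 14.5% at n=50 and 8.3% at n=150. The slip is therefore confined to the second half of item 2.

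**2. Normal intervals for normally distributed data.** Coverage = P(|t(n−1)| < 1.96): about 94.0% at n=30, 94.4% at n=50, and 91.8% at n=10. The last is an assumed size for a stratum with no minimum. The normal half-width is 0.958 of the t half-width at n=30 and 0.975 at n=50.

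**3. Normal intervals for a clustered 0-4 score.** This step assumes five whole-number categories. Coverage is simulated with 400,000 samples per setting (200,000 for the 85% row). The chance of zero width is the sum over categories of (category probability)^n. Shares are listed from the best category to the worst; which end of the scale is best does not affect coverage.

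| Assumed shares (%) | Coverage n=30 / n=50 | Zero width n=30 / n=50 |
|---|---|---|
| 10/20/40/20/10 | 94.0% / 94.4% | negligible |
| 50/30/12/6/2 | 92.8% / 93.7% | negligible |
| 70/20/7/2/1 | 90.9% / 92.2% | negligible |
| 80/14/4/1/1 | 87.8% / 90.1% | 0.12% / 0.001% |
| 85/10/3/1/1 | 85.7% / 88.3% | 0.8% / 0.03% |
| 90/7/2/1/0 | 85.6% / 87.9% | 4.2% / 0.5% |
| 95/4/1/0/0 | 78.5% / 76.0% | 21.5% / 7.7% |

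A second distribution with 70% at best gave 90.2% / 92.3%.

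**4. Does t cure the clustering?** Not reliably. With 90% at best, coverage moves from 85.6% to 85.7% (n=30) and from 87.9% to 88.0% (n=50). With 80% at best it moves from 87.8% to 90.2% and from 90.1% to 91.6%. With 95% at best it stays at 78.5% for n=30 but jumps from 76.0% to 92.2% for n=50, an effect of the few values the mean can take. A t interval still has zero width when all scores agree.

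**5. The exact interval.** Applied to the share of participants not at the best value, it keeps its width: 0 of 30 gives 0 to 11.6%, and 0 of 50 gives 0 to 7.1%.

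**The case against.** A reader might infer that the planned intervals will be too narrow because scores must cluster at the best value, and that they will collapse to zero width. The documents do not support that, for four reasons.

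- Section 13 is a general rule. Nothing assigns the mean and its interval to the 0-4 score; a frequency table with exact intervals is equally open under the same section.
- The scale appears only in the change order, where it is called a VAS. Items, anchors and direction are not given. If marks can fall between whole numbers, ties and zero widths become less likely.
- Clustering is an inference. Section 2.3 reports that "none of the participants reported any issues with swallowing" the capsule, but goes on to say those studies were in young healthy volunteers. Excluding people with pill-swallowing issues (Section 7.2.2) makes good scores plausible, but the questionnaire also covers palatability (Section 7.7.3), and Section 7.7.4 provides for failed swallows.
- The large losses come only from strong assumed ceilings. With up to 50% at the best value the loss is about 1 to 2 points.

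It is also fair to say that 27.7% is correct for the stated method, that the normal-versus-t difference is small, and that the median, minimum and maximum will accompany each mean, so a collapsed interval would be visible.

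All of this stands, and it limits the clustering argument to a conditional one. It does not touch the wrong figure at 200, nor the small shortfall of normal intervals in groups of this size.

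**Conclusion.** Section 13.2 item 2 needs correcting whatever view is taken of the score. At 200 the half-width is 13.9% of the SD; 16.0% is the value at 150. The printed figure is too large for its stated n by a factor of √(200/150) = 1.15. At most 150 participants can contribute to a post-swallow mean.

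The normal intervals cost about half a point to one point of coverage at n=50 and n=30 for normally distributed data, and about 3 points at an assumed n=10.

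A larger loss requires two things that the documents leave open: that the 0-4 score is reported as a mean, and that it clusters. Under the assumed five-category distributions, coverage at n=30 to 50 is then about 90-92% with 70% at the best value and 86-88% with 85-90%. Zero width is a practical risk at these sizes only from about 90% upward.

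The consequence is limited: the study is descriptive and no decision rule uses these intervals. They would, however, be its main statement of uncertainty for any subgroup mean.

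**What to change.** 1. In Section 13, replace asymptotic intervals for means with t intervals.
2. Restate Section 13.2 item 2 as ±28.4% of the SD at n=50 and ±16.1% at n=150. If normal intervals are kept, state 27.7% at n=50 and 16.0% at n=150.
3. State in Section 13 how the 0-4 post-swallow score is recorded and analysed. If it is recorded in discrete categories, summarise it by counts and percentages per category with the exact intervals already planned for proportions, since t alone does not cure a ceiling.

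The cost is a few lines of text and code, and slightly wider stated and reported intervals.

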### **13.1 Analysis Cohorts**

All participants who attempt to swallow the Mock-RP in the study are included in the Analysis Cohort used for evaluating swallowability of the Mock-RP.

### **13.2 Sample Size Justification**

As an observational study, no hypothesis tests are planned. All data will be summarized. Nevertheless, with the sample size proposed for the study, the following levels of precision of the estimates, expressed as the width of the confidence interval, can be achieved:

1. The width of the exact 95% two-sided confidence interval for percentages will be no wider than +/- 14.5% with 50 participants contributing to the estimate of the proportion and will be no wider than +/- 8.3% with 150 participants.
2. The width of the 95% two-sided confidence interval for the mean will be equal to +/- 27.7% of the standard deviation with 50 participants contributing to the estimate of the mean and will be equal to +/- 16.0% of the standard deviation with 200 participants.

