### 1.2 Study Scope

This study will be conducted at one site in the U.S. Up to 200 participants will be enrolled (consented) and up to 150 will attempt to swallow the Mock-RP after passing protocol required screening. Study duration is expected to be approximately three months.

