## 5 STUDY SAMPLE SIZE

As a prospective, single-center, open-label, single-arm, observational study, no statistical criteria for sample size are required. A total of 30 to 50 participants in each age group (21-50, 51-65, 66-75), for a total of up to 150 participants will provide sufficient data to characterize the endpoints, as well to evaluate swallowing trends between subgroups.

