### 7.6.2 Clinical Examination

A medical history focusing on, but not limited to, the 90 days before study day will be obtained. The history will review the use of medications, including prescription and non-prescription pharmaceuticals per Section 7.6.3 “Concomitant Medications, Treatments, and Procedures”.

Height, weight, and temperature will be measured before administration of the Mock-RP capsule.

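### Section 13.2 pairs a mean confidence interval of ±16.0% of the SD with 200 participants; 200 gives ±13.9%, and 16.0% is the value for 150

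*Combined protocol and SAP*

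**What the plan says.** Section 13.2 states that no hypothesis tests are planned and then gives four precision figures, two for percentages and two for means.

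- Item 1 covers percentages by exact intervals: ±14.5% with 50 participants, and the interval "will be no wider than +/- 8.3% with 150 participants".
- Item 2 covers means. It begins "The width of the 95% two-sided confidence interval for the mean will be equal to +/- 27.7% of the standard deviation with 50 participants", and for the larger number it says the interval "will be equal to +/- 16.0% of the standard deviation with 200 participants".

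The method for means is fixed in Section 13: "Asymptotic confidence intervals will be generated for estimates of means".

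The two candidate totals are separated in Section 1.2: "Up to 200 participants will be enrolled (consented) and up to 150 will attempt to swallow the Mock-RP after passing protocol required screening". Section 5 builds the sample size from "A total of 30 to 50 participants in each age group (21-50, 51-65, 66-75), for a total of up to 150 participants". Under Section 13.1, those who attempt to swallow the capsule "are included in the Analysis Cohort used for evaluating swallowability of the Mock-RP".

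**The concern.** Item 1 evaluates precision at 50 and 150, while item 2 uses 50 and 200. The change in the larger number is not explained, and the percentage beside it does not belong to 200. From 50 to 200 the sample size is multiplied by four, so the half-width should halve. Going from 27.7% to 16.0% is not a halving.

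At stake is whether the plan's only numerical account of precision is correct. As the sentence stands, a reader cannot be certain whether the number of participants or the percentage is the slip, nor which set of participants the mean describes. No sample size, test or decision is derived from the figure.

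**Working it through.** **Inputs.** Confidence level 95%, two-sided (Section 13.2), so z = 1.95996. Asymptotic interval for a mean (Section 13). Sample sizes 50, 150 and 200 (Sections 1.2, 5 and 13.2). The plan speaks of width but writes the figures as ±, so they are treated as half-widths.

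**Formula.** Half-width as a fraction of the SD = z/√n.

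**Reproducing the plan's own figure.** At n = 50: 1.95996/√50 = 27.72%. This matches the stated 27.7% and confirms the formula. A t quantile gives 28.42% and does not match.

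**The figure in question.**

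| n | Normal quantile | t quantile | Plan |
|---|---|---|---|
| 50 | 27.72% | 28.42% | 27.7% |
| 150 | 16.00% | 16.13% | not given |
| 200 | 13.86% | 13.94% | 16.0% |

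**Solving backwards.** Setting z/√n = 0.160 gives n = (1.95996/0.160)² = 150.06. With unrounded z, the values of n that round to 16.0% run from 149.12 to 150.999, so 150 is the only whole number in the range.

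**Check from the plan's own number, without choosing z.** Scaling the stated 27.7% at n = 50 gives 27.7%/√(200/50) = 13.85% at 200 and 27.7%/√(150/50) = 15.99% at 150.

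**Other confidence levels at n = 200.** 90% gives 11.63%, 98% (by t) gives 16.58% and 99% gives 18.21%. A half-width of 16.0% would need a level of about 97.6%, but the text says 95%.

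**Item 1.** The largest Clopper-Pearson half-width over all possible counts is 14.47 percentage points at n = 50 and 8.26 at n = 150. These agree with the stated 14.5% and 8.3%.

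**Which population.** At most 150 participants attempt to swallow, and they form the cohort for swallowability, so no mean from that cohort can rest on 200. A mean over 200 would need a variable recorded on everyone who consented. Height and weight are possible examples: "Height, weight, and temperature will be measured before administration of the Mock-RP capsule" (Section 7.6.2). The plan does not say that they are recorded for people who consent and then fail screening. Even for such a variable, 16.0% would be wrong at 200.

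**The case against.** The strongest reply is that this is close to a typing error with no consequence. The study tests nothing, Section 5 says no statistical criterion for the sample size is needed, and the figure is correct if 150 contribute and cautious if 200 do. A reader who checks the arithmetic will probably conclude that 150 was meant. All of this stands and limits the point to a minor one. It does not make the sentence right. Item 2 says the interval will equal the stated value, unlike item 1, which gives an upper bound, so 16.0% cannot be defended as a conservative limit.

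A narrower objection is that the uniqueness of n = 150 depends on the precision of z. With z cut to 1.96, n = 151 gives 15.9503%, which also rounds to 16.0%; with unrounded z it gives 15.94996%, which does not. That is correct but immaterial: the main result is that 200 gives 13.9%, and 151 is not a planned number.

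The plan also allows as few as 30 per age group, or 3 × 30 = 90 overall, where intervals can be wider than those shown. Each figure in Section 13.2 is conditional on its own n, so this is not an error in the section and the correction does not depend on it.

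**Conclusion.** The figure is wrong as written. By the plan's own method, the half-width for a mean with 200 participants is 13.9% of the SD, not 16.0%, a difference of 2.1 percentage points of the SD. The value 16.0% belongs to 150 participants. The conclusion rests only on the stated 95% level and the asymptotic interval, and using t instead does not change it.

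That 150 was intended is an inference. It is well supported by the exact numerical match, by item 1 and by the cap on swallow attempts, but the documents do not state it. The matter is minor. If 200 participants did contribute, the sentence understates precision; if 150 did, the precision is right and only the number of participants is wrong.

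**What to change.** In Section 13.2, item 2, replace 200 with 150 and leave 16.0% as it is. This agrees with item 1 and with the cohort in Section 13.1. If a mean over all consented participants was intended, keep 200, replace 16.0% with 13.9%, and state which variables are collected on that full set.

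The cost is one number in one sentence, plus a short clause under the second option. Enrolment, data collection and analysis do not change.

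Optionally, the sponsor could label the present figures as those for full enrolment, or add the values at minimum enrolment: for percentages, at most ±18.7% with 30 and ±10.7% with 90; for means, ±35.8% of the SD with 30 and ±20.7% with 90.
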